For each cohort and each calendar month, the study population will consist of people who have a record of asthma or COPD. For the asthma cohorts, each monthly cohort will consist of those patients who, on the 15th of each month (the index date), had 1) their first asthma code on or before that date; and 2) did not have COPD on or before that date.³⁹ Correspondingly, for the COPD cohorts, each monthly cohort will consist of those patients who, on the 15th of each month, had 1) their first COPD code on or before that date; and 2) did not have asthma on or within 3 years before that date. To be included in a cohort, patients must have at least one year of follow-up in CPRD prior to the index date and have age and gender recorded in CPRD.

Comparative cohort studies

For the comparative cohort studies, the study population will consist of two separate, mutually exclusive disease cohorts, a COPD cohort and an asthma cohort, consisting of patients registered with GP practices meeting CPRD quality control standards. For each disease cohort (asthma and COPD), two cohorts will be created, one for the first wave of COVID-19 and one for the second, defined relative to a cohort entry date (1st March 2020 for wave 1, 1st September 2020 for wave 2), to make a total of four cohorts. To be included in a cohort, patients must have at least one year of follow-up in CPRD prior to the cohort entry date, be eligible for linkage to HES data, and have gender and age recorded in CPRD.

Asthma cohort⁴⁰

The asthma cohort will include all adults aged 18 and over with a recorded diagnosis of asthma defined as a record of asthma within 3 years prior to the cohort entry date. This method of identifying asthma has previously been validated in CPRD.⁴⁰ Code lists to identify asthma will be reviewed by a clinical expert before use.

Patients will be excluded if they have a record of COPD or any other chronic respiratory condition at any point before the cohort entry date, or a prescription of a LAMA but no ICS within 3 years before the cohort entry date, as this indicates possible COPD. Patients who received a prescription of nebulised medication within 1 year before the cohort entry date will also be excluded, as this indicates very severe asthma.

COPD cohort⁴¹

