before the previous one is estimated to have been completely used, we will assume stockpiling occurred and assign the maximum total days of exposure possible with the combined prescriptions. Patients who switch treatment groups will be considered exposed to the active comparator/ICS group from the date of the switch, and those who discontinue treatment or switch to a treatment not under study will be censored at discontinuation or switch.

Patients will be considered exposed from the date the prescription was issued, as ICS have been shown to exert anti-inflammatory effects within hours of administration.⁴³

Outcomes

- SARS-CoV-2 infection, defined as a recorded positive test for SARS-CoV-2 in the primary care record sourced from the Second Generation Surveillance System (SGSS).
- hospitalisation with COVID-19, defined as admission to hospital with an ICD-10 code for COVID-19, ascertained using HES data.
- death with COVID-19, defined as death with an ICD-10 code for COVID-19 listed as an underlying or contributing cause of death in the ONS death registry.

Covariates

- demographic and lifestyle variables at baseline: age, sex, body mass index (BMI), smoking status, ethnicity, socioeconomic status (Index of Multiple Deprivation, IMD)
- ever-present comorbidities at baseline: chronic kidney disease, hypertension, heart failure, other heart diseases, diabetes, cancer, immunosuppression
- time-updated covariates: influenza vaccination within one year before the cohort entry date, pneumococcal vaccination within 5 years before the cohort entry date, vaccination against COVID-19 (wave 2 only)
- calendar time, COVID-19 prevalence figures (ONS)
- asthma cohort only: number of recorded asthma exacerbations (emergency department visit, hospitalisation or prescription of an oral corticosteroid for asthma⁴⁴) within 1 year before the cohort entry date
- COPD cohort only: number of recorded COPD exacerbations (defined using a validated algorithm⁴⁵) within 1 year before the cohort entry date.

O. Data analysis

Descriptive study:

Population-level measures of ICS use that will be determined per calendar month are:

- Number and proportion of incident and prevalent users over the course of follow-up for each calendar month:
 - Prevalent ICS exposure will include people with an ICS prescription recorded on any day during that month.

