- Incident ICS exposure will be defined as a new ICS prescription with no prescription in the previous 6 months. Prevalent users will therefore also include incident users.
- The denominator will be all people with asthma or COPD in each month **Error!**

Reference source not found..

- Number of individual prescriptions per person per month (absolute number).
- Dosages prescribed: median or mean daily dose among those prescribed ICS for any given month.
- Discontinuation of ICS or date of treatment switch: number and proportion of people who have ≥ 6 months of no ICS-containing inhaler prescription.

This study will be descriptive. Results will be presented as absolute numbers and proportions as bar graphs.

The results from this study will inform the exposure definition that will be used in the comparative cohort study (see section on Exposure definitions). This study will be completed before starting the analyses for the subsequent comparative cohort studies.

Comparative cohort studies:

We will conduct descriptive analyses (frequency, percentages, mean [SD] and median [IQR]) to assess characteristics of the patients in each cohort, stratified by exposure group at baseline. Categorical variables will be compared using χ^2 tests. Continuous variables will be compared using t-tests for normally distributed variables and Mann-Whitney test for non-normally distributed variables. Time to each outcome will be presented using Kaplan-Meier plots using time in study as the time scale.

Propensity scores will be generated using logistic regression to estimate likelihood of ICS prescription based on baseline characteristics. All pre-specified covariates will be included in the logistic regression.

The association between ICS prescription and each outcome will be estimated using a Cox regression model to calculate hazard ratios and 95% CIs, using time in study as the time scale. Univariable models, models adjusted for age and sex, and propensity score weighted models will be presented. Schoenfeld residuals will be used to graphically assess the validity of the proportional hazards assumption. If the proportional hazards assumption is violated, we will use interaction terms between the exposure and time to describe any variations in the hazard ratio over time.

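### In the descriptive study, patients first coded (or completing their registration year) after the 15th who start ICS that same month are never counted as incident users

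*Protocol*

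**What the plan says.** Section L (Study population, Descriptive study) sets membership at one date per month: "For the asthma cohorts, each monthly cohort will consist of those patients who, on the 15th of each month (the index date"). The entry test for asthma is "their first asthma code on or before that date", together with no COPD by then. The COPD cohort follows the same pattern ("their first COPD code on or before that date"), with its own exclusion for recent asthma. The registration rule uses the same date: "patients must have at least one year of follow-up in CPRD prior to the index date".

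Section O (Data analysis, Descriptive study) works with a different window. Its first output is "Number and proportion of incident and prevalent users over the course of follow-up for each calendar month". For prevalent use, the window is the full month: "Prevalent ICS exposure will include people with an ICS prescription recorded on any day during that month". For incident use, a look-back applies as well: "Incident ICS exposure will be defined as a new ICS prescription with no prescription in the previous 6 months". The section then makes clear that the two groups are nested: "Prevalent users will therefore also include incident users".

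No rule carries a start made after the 15th into the next month, and nothing limits the 6-month look-back to time spent in the cohort. The denominator sentence in section O refers to everyone with the disease in the month and does not repeat the 15th. Section L is the only explicit definition of the monthly population.

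**The concern.** Eligibility is judged on the 15th, but events are counted to the end of the month. Someone who becomes eligible on the 16th or later and starts ICS before the month ends falls between the two rules. They are too late for the current month's cohort, and by the next month the look-back disqualifies them.

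The number and proportion of incident ICS users are named outputs of the descriptive study, which serves Objective A. The error runs in one direction, does not shrink with sample size, and falls on one group: people who start ICS at or soon after diagnosis, or soon after completing a year of registration.

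**Working it through.** The protocol states no incident-user count, so there is no figure to reproduce. The check follows the rules by date and then counts days.

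**Inputs.** From section L: membership on the 15th and follow-up from 1 March 2019 to 30 April 2021. From section O: prescriptions on any day of the month and a 6-month look-back (183 days in the trace).

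**Date trace**

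| Patient | Result |
|---|---|
| First code and first ICS on 20 June, repeats every 30 days | Not in the June cohort. In the July cohort, but the June prescription is inside the look-back. Never incident |
| First code 10 June, first ICS 20 June | Counted in June |
| First code 20 June, first ICS 5 July | Counted in July |
| First code and first ICS 20 June, then nothing until 10 February | Only the February restart is counted. The true start is lost |
| ICS 3 June, first code 20 June, repeat 3 July | Never incident |

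The first two patients start ICS on the same day. Only the date of the first code differs.

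**Share of same-day starts lost.** In a month of L days this is (L − 15)/L:

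- 28 days: 13/28 = 46.4%
- 29 days: 14/29 = 48.3%
- 30 days: 15/30 = 50.0%
- 31 days: 16/31 = 51.6%

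The 26 months comprise fifteen of 31 days, nine of 30, one of 29 and one of 28.

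- Days after the 15th: 15×16 + 9×15 + 14 + 13 = 402
- All days: 15×31 + 9×30 + 29 + 28 = 792
- Overall: 402/792 = 50.8%

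**Effect of a delay from diagnosis to first ICS.** With a fixed delay of d days and diagnoses spread evenly, the days lost per month are max(0, L − 15 − d):

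- d = 3: 15×13 + 9×12 + 11 + 10 = 324; 324/792 = 40.9%
- d = 7: 15×9 + 9×8 + 7 + 6 = 220; 220/792 = 27.8%
- d = 14: 15×2 + 9×1 = 39; 39/792 = 4.9%
- d = 21: none

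With exponentially distributed delays of mean 3, 7, 14, 30 or 60 days (200,000 simulated patients), the loss is about 42%, 32%, 21%, 12% or 6%. The delay is not given in the protocol, and its assumed form clearly matters: 14 days gives 5% if fixed and 21% if exponential.

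**Effect on the total incident count.** Suppose a share p of all incident users start on the day of diagnosis and all other starts are counted. The count is then too low by p × 0.508:

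- p = 5%: 2.5%
- p = 10%: 5.1%
- p = 25%: 12.7%

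The mid-month denominator is unchanged, so the incident proportion falls by the same relative amount. The protocol does not give p.

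**The case against.** The strongest reply is that a mid-month population is a legitimate choice, namely ICS use among people already diagnosed on the 15th, and that the loss is narrow and steady. Most of this stands. The share of days after the 15th is between 46.4% and 51.6% in every month. The rule therefore lowers the level of the incident series but largely preserves its shape, unless the share of newly diagnosed starters or the timing of starts within the month shifts. The incident pool also includes everyone who restarts after 6 months without ICS, so newly diagnosed starters are only one part of it. What does not stand is the idea that the choice is coherent for incident use: the numerator runs past the eligibility date, and the look-back then removes the same people from the next month.

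A second reply is that the broader denominator wording in section O might bring in patients diagnosed later in the month. It does not displace the explicit definition in section L. At most it shows that the two sections need aligning.

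Three stronger readings are tempting, and the protocol does not support them.

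- **A late-March 2020 surge would be hidden.** Anyone coded by 15 March with the registration year complete is in the March cohort, and their prescriptions on any day of March count. That covers patients who stockpile, restart or start late in the month. Section N looks for a rise in prescriptions that would suggest stockpiling, which concerns people already treated. The choice between time-fixed and time-updated exposure is therefore barely touched.
- **Half of all incident users are lost.** The one-half applies only to people who start on the day of diagnosis.
- **The hazard ratios or Table 1 are biased.** The comparative cohorts use their own entry dates, so the monthly rule does not reach them directly.

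**Conclusion.** The mismatch is real and follows from the wording of sections L and O. It affects patients whose first disease code, or completion of one year's registration, falls after the 15th and who start ICS in that same month. Their initiating prescription is never incident, and they can reappear only as re-starters after a 6-month gap. Prevalent counts miss them only in the month they first qualify, provided later prescriptions follow.

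About half of same-day starters are lost, assuming diagnoses are spread evenly over the month, and fewer with longer delays. The effect on the total is modest over the range examined, about 2.5% to 13%, and rests on an assumed share of 5% to 25% same-day starters. This is a one-directional error in a named descriptive output. It is worth correcting before the analysis starts but does not threaten the comparative study.

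**What to change.** Keep the 15th as the date for the denominator. For the incident and prevalent numerators, assess every membership condition (first disease code, cross-disease exclusion, one year of registration) at the date of the ICS prescription, in both the asthma and COPD cohorts. Reword the denominator sentence in section O so that it names the mid-month population of section L.

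Assessing the conditions on the last day of the month is a different rule. It would also admit ICS issued before a first code later in the same month, as in the last row of the trace, which the prescription-date rule leaves out. The protocol should state one rule only.

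The cost is about one sentence in each of sections L and O and a small code change. The numerator is then no longer strictly nested in the mid-month denominator. That is negligible at these cohort sizes: the feasibility counts in section J, made under somewhat different criteria, are 755,632 patients with asthma and 225,472 with COPD.

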D. Aims, objectives, rationale

The aim of this study is to investigate the effects of ICS at different stages of the COVID-19 disease pathway (i.e., infection, hospitalisation, and death) among patients with asthma or COPD and apply methods of QBA to these effect estimates to account for potential biases arising in these estimates of association. The null hypothesis is that use of ICS has no effect on COVID-19-related outcomes.

Objectives

- A. To describe prescription patterns of ICS among patients with respiratory diseases before and during the COVID-19 pandemic.
- B. To investigate the association between prevalent ICS use and COVID-19 related outcomes among patients with respiratory diseases.
 - a. Estimate the association between prevalent ICS use and risk of having a positive SARS-CoV-2 test.
 - b. Estimate the association between prevalent ICS use and risk of hospitalization with COVID-19 among patients with a positive SARS-CoV-2 test.
 - c. Estimate the association between prevalent ICS use and risk of death among patients who were hospitalized with COVID-19.
- C. To develop approaches and apply methods of QBA to account for potential biases arising in these estimates of association.
 - a. Investigate impact of exposure misclassification (e.g., due to stockpiling of medication, patients not filling prescription or underascertainment of in-hospital medication use) on estimates from objective 2a, 2b, and 2c.
 - b. Quantify potential biases due to unmeasured or unknown confounders on estimates from objective 2a, 2b, and 2c.
 - c. Investigate impact of outcome misclassification (e.g., underascertainment of infections due to limited testing availability and non-random testing) on estimates from objective 2a.
 - d. Investigate impact of selection bias (e.g., non-random selection of individuals into a study) on estimates from objective 2b and 2c.

E. Outcomes

COVID-19 positive test result; hospitalisation with COVID-19; death with COVID-19, as defined in section N.

F. Study type

The overall study design is a historical cohort study.

G. Study design

Objective 1 will be a descriptive study with a population-level description of prescription patterns of ICS before and during the COVID-19 pandemic among patients with respiratory disease.

Objective 2 will be a hypothesis testing cohort study. The null hypothesis is that there is no association between ICS use and testing positive for COVID-19, hospitalisation for COVID-19 and death with COVID-19.

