The COPD cohort will include all adults aged 35 and over with a recorded diagnosis of COPD at any point before the cohort entry date.⁴¹ This method of identifying COPD has previously been validated in CPRD.⁴¹ Code lists to identify COPD will be reviewed by a clinical expert before use. To be included, patients must also have a record of current or former smoking in CPRD.

As in the asthma cohort, patients who have a record of other chronic respiratory conditions at any point before the cohort entry date will be excluded. People who use a leukotriene receptor antagonist (LTRA) within 3 years of the cohort entry date will be excluded as this indicates asthma, as will people who are prescribed a LABA/LAMA and ICS within 3 months before the cohort entry date, as this indicates severe COPD.

Censoring

For all cohorts, cohort exit will be defined as the first of either occurrence of the outcome (for each analysis), death, disenrollment from GP practice, the last date of data availability, or the end of the COVID-19 wave (31st August 2020 for wave 1, 30th April 2021 for wave 2).

M. Comparator groups

The study will use an active comparator group including all people with recorded asthma within 3 years or COPD at any point before the cohort entry date (1st March 2020 or 1st September 2020, respectively) who received a prescription for inhaled medication for asthma or COPD, but no ICS prescription.

The comparator group for the asthma cohort will be people who were not prescribed medication containing ICS and were prescribed a non-ICS inhaled medication for asthma. For the COPD cohort, the comparator group will include people who were not prescribed a medication containing ICS and were prescribed a LABA/LAMA separately or in combination for COPD. Exposures and exposure durations in the comparator group will be calculated in the same way as in the ICS-exposed group.

N. Exposures, outcomes and covariates

Exposure

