If a time-updated exposure definition is used, we will account for potentially informative censoring using inverse-probability of censoring weights. Propensity scores will also be time-updated to account for time-dependent confounding.

A number of sensitivity analyses/additional analyses will be conducted:

- Stratification by ICS dose (low/medium vs higher)
- Do not condition on positive test (2b) or hospitalisation (2c), in order to repeat published analyses

- Include people with a diagnostic code for COVID-19, or a code that implied SARS-CoV-2 infection, but no registered positive SARS-CoV-2 test

P. Quantitative Bias Analysis

Quantitative Bias Analysis Method:

We will use probabilistic bias analysis to quantify the effect of biases on the effect estimates in objectives 2a-c. In probabilistic bias analysis, each bias parameter is assigned a distribution which reflects the uncertainty around the specific value for the parameter. The bias parameters are sampled repeatedly from this distribution and applied to the observed effect measure to obtain a bias-adjusted point estimate and simulation interval.^{22,46} For research questions where more than one bias may have a significant impact, we will also conduct multiple bias modelling to obtain effect estimates that are adjusted for several biases.

Misclassification:

We will use a range of plausible values for sensitivity and specificity of the outcome and exposure classification to adjust for outcome and exposure misclassification, respectively.

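### The wave 2 cohorts neither exclude nor adjust for recorded SARS-CoV-2 infection or COVID-19 admission before 1 September 2020, and objectives 2b and 2c do not date the qualifying test or admission.

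*Protocol*

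**What the plan says.** Section L (Comparative cohort studies) states that for each disease "two cohorts will be created, one for the first wave of COVID-19 and one for the second", with entry dates of "1st March 2020 for wave 1, 1st September 2020 for wave 2), to make a total of four cohorts". One inclusion rule serves both waves: "patients must have at least one year of follow-up in CPRD prior to the cohort entry date, be eligible for linkage to HES data", plus recorded age and gender.

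The exclusions concern respiratory disease and its drugs. For asthma: "Patients will be excluded if they have a record of COPD or any other chronic respiratory condition at any point before the cohort entry date", with further rules on LAMA without ICS and on nebulised medication. For COPD: "patients who have a record of other chronic respiratory conditions at any point before the cohort entry date will be excluded", with further rules on LTRA and on LABA/LAMA with ICS. None mentions an earlier positive test, COVID-19 code or COVID-19 admission. The exit rule under Censoring works within each cohort, so a wave 1 event does not bar entry to wave 2.

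Section N defines infection as a recorded positive test and hospitalisation as an admission carrying a COVID-19 code. Neither is limited to a first event, and no minimum interval separates a new infection from an old one. The COVID-19 items among the covariates are "vaccination against COVID-19 (wave 2 only"), calendar time and ONS prevalence figures. None is an individual's infection history.

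Section D sets objective 2b (listed there as B.b) as the "risk of hospitalization with COVID-19 among patients with a positive SARS-CoV-2 test". Objective 2c conditions on COVID-19 hospitalisation in the same way. Neither gives a date window for the qualifying event.

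**The concern.** A cohort for time to infection should start with people at risk of a new infection. Someone who tested positive in spring 2020 enters wave 2 on 1 September with a probably lower hazard, and a late or repeat positive from that illness would be counted as a wave 2 event. The protocol adjusts for vaccine-derived protection in wave 2 but not for protection from infection. If earlier infection differs by ICS use, it confounds the wave 2 comparison.

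The planned bias analysis does not cover this. Section P treats missed infections as outcome misclassification in 2a and as selection into 2b, not as earlier immunity. Section T does not list it.

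For 2b and 2c the issue is the missing date. Taken literally, a survivor of a wave 1 test or admission meets the wave 2 definition while having little chance of the event. These populations are far smaller than the full cohorts, so the same number of old cases would weigh more. The 2c selection probabilities, which section P derives from HES admissions, would carry the same ambiguity.

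**Working it through.** **Inputs from the protocol.** Section K: 295,134 positive tests and 36,974 COVID-19 deaths in England from March to August 2020, population 56,550,000. Section J: 755,632 asthma and 225,472 COPD patients; ICS shares 64.2% and 37.1%. Table 1: ICS share 64%.

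**1. The protocol's own figure.** 295,134 / 56,550,000 = 0.522%; section K states 0.52%. It reproduces.

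**2. Recorded wave 1 positives in the cohorts.**
- Asthma: 0.005219 × 755,632 = 3,944.
- COPD: 0.005219 × 225,472 = 1,177.

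The dead cannot enter wave 2. If all deaths were among test positives, the rate is (295,134 − 36,974) / 56,550,000 = 0.457%, giving about 3,450 asthma and 1,030 COPD patients. These figures count tests as persons, apply a general-population rate (section K assumes that these patients' rate is equal or higher), and precede the respiratory, linkage and inhaler criteria.

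**3. Effect on 2a.** Assume a true HR of 1, full immunity after infection, and wave 1 infection r times as common in ICS users. With p the earlier-infection share in the comparator group, observed HR ≈ (1 − r·p) / (1 − p).

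| p | r = 1.0 | r = 1.2 | r = 1.5 |
|---|---|---|---|
| 0.522% (recorded only) | 1.000 | 0.999 | 0.997 |
| 5.22% (assumes 10 times as many true infections) | 1.000 | 0.989 | 0.973 |

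The values of r and the multiple of 10 are assumptions. With r below 1 the HR would move up. The second row is mostly undetected infection, which no exclusion based on records can reach.

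**4. Share of an undated 2b pool.** Share = wave 1 rate / (wave 1 rate + wave 2 rate), with wave 2 recorded positivity assumed to be 3-6%.
- Without removing deaths: 0.52 / 6.52 = 8.0% and 0.52 / 3.52 = 14.8%.
- With deaths removed: 0.457 / 6.457 = 7.1% and 0.457 / 3.457 = 13.2%.

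**5. Direction in 2b.** Suppose the old cases have no events and 64% of new positives use ICS, so the ICS to comparator ratio is 64/36 = 1.778. Old cases change only the denominators. The HR is multiplied by 1.778 divided by the ratio in the mixed pool.

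| ICS share in old cases (assumed) | Old cases 8.0% of pool | Old cases 14.8% of pool |
|---|---|---|
| 74% | 1.778 / 1.841 = 0.97 | 1.778 / 1.897 = 0.94 |
| 64% | 1.00 | 1.00 |
| 54% | 1.778 / 1.717 = 1.035 | 1.778 / 1.668 = 1.066 |

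**6. Power cost of an exclusion.** Schoenfeld's formula, with 0.52% of patients having the event and the ICS shares of section J. Removing 0.52% of patients takes asthma power at HR 1.1 from 81.7% to 81.5%, and COPD power at HR 1.2 from 85.4% to 85.3%.

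**The case against.** The strongest reply concerns 2b and 2c. Section B runs every analysis separately by wave. Section L ends each cohort's follow-up at the end of its wave. Section P ties selection into 2b to misclassification of the 2a outcome, which is counted during wave follow-up. Section D describes successive stages of one disease pathway. Together these favour qualifying events inside the wave. That stands: the text permits older events but does not say they will be used, and a statistical analysis plan may date them.

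A reader might infer that old cases will enter 2b and 2c and pull the wave 2 HR down. The documents support neither step. The sign depends wholly on the ICS share among old cases, for which they give no figure. Nor do they show that infection leads to ICS prescribing in particular: both arms are defined by inhaled prescriptions, so a new non-ICS inhaler would place a patient in the comparator group. The three-month exposure window before entry applies only if the time-fixed definition is chosen, which section N leaves open.

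It is also fair to say that the clear omission, in 2a, has a small effect, and that limited wave 1 testing means an exclusion catches only some earlier infections. Neither point defends leaving known earlier cases in the risk set. Eligibility and covariates are matters that sections L and N set out themselves, so the omission is not simply detail left for later.

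**Conclusion.** The point holds as a low-priority correction. Wave 2 counts people with recorded earlier infection as at risk, has no covariate for it, and lets a residual wave 1 positive count as a wave 2 event. About 0.5% of each cohort is affected on recorded tests, and the effect on the 2a HR is under about 1% (0.1% to 0.3% under the assumptions shown). The number of repeat positives counted as new cannot be estimated from the protocol.

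For 2b the result is conditional. If undated tests were admitted, wave 1 positives could be roughly 7-15% of the pool at an assumed wave 2 positivity of 3-6%. The bias could go either way and is near zero if ICS use is equal in old and new cases. For 2c the same gap in dating exists, but no size can be given. It should not be claimed that wave 2 estimates in 2b and 2c are biased, or biased in a known direction. What is established is that the text leaves this open.

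**What to change.** Make two changes in section L:

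- Add to wave 2 eligibility: no recorded positive test, no COVID-19 diagnostic or implied-infection code, and no COVID-19 admission before 1 September 2020.
- State that the index test (2b) or index admission (2c) must fall within the wave, and that follow-up in those analyses starts at that event. Apply the same dating to the HES-based selection probabilities for 2c in section P.

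The data and code lists are already needed: section O plans a sensitivity analysis that adds people with a COVID-19 diagnostic code "or a code that implied SARS-CoV-2 infection, but no registered positive SARS-CoV-2 test".

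The cost is about 0.5% of patients on recorded tests, somewhat more once codes and admissions are included. Power falls by about 0.2 percentage points at most for the loss on recorded tests. Undetected earlier infections remain; list them in section T or give them a parameter in the section P bias analysis.

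### In objective 2b, COVID-19 death without admission is censored and no companion analysis shows these deaths, so the admission hazard ratio can mislead in either direction and Kaplan-Meier overstates admission risk

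*Protocol*

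**What the plan says.** Section D (where objectives 2a to 2c appear as B.a to B.c) sets a sequence of conditional questions. Objective 2b concerns "risk of hospitalization with COVID-19 among patients with a positive SARS-CoV-2 test". Objective 2c concerns "risk of death among patients who were hospitalized with COVID-19".

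Section N defines the 2b event as "hospitalisation with COVID-19, defined as admission to hospital with an ICD-10 code for COVID-19, ascertained using HES data". The death outcome is "death with an ICD-10 code for COVID-19 listed as an underlying or contributing cause of death in the ONS death registry", with no restriction on place of death or prior admission.

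Section L, under Censoring, states for all cohorts that "cohort exit will be defined as the first of either occurrence of the outcome (for each analysis), death, disenrollment from GP practice", along with the end of data and the end of the wave.

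Section O specifies Cox models and says: "Time to each outcome will be presented using Kaplan-Meier plots using time in study as the time scale". It reserves inverse-probability-of-censoring weights for a time-updated exposure. It also lists an additional analysis without conditioning on a positive test (2b) or on hospitalisation (2c).

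Section P describes selection-bias analyses. The one for 2b draws on missed infections. The one for 2c uses HES, CPRD and ONS data to estimate the probability of admission by exposure and death.

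**The concern.** The study aims to separate effects at infection, hospitalisation and death. A COVID-19 death without admission is an outcome under the protocol's own death definition, yet neither conditional step counts it. In 2b the patient leaves the risk set at death without an event. In 2c the patient never enters.

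If one exposure group has a larger share of its severe outcomes as deaths without admission, its admission hazard is lower for that reason alone. A reader who takes the 2b result as an effect on severe disease, or on the risk of hospitalisation as the objective puts it, could see protection or harm that reflects only where patients died. Section P addresses selection bias in 2b only through missed infections, so this mechanism is not covered there.

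The Kaplan-Meier plot is a separate matter. Treating death as censoring estimates admission as if those who died could still be admitted. It therefore overstates the probability of admission, and this needs no difference between the groups.

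**Working it through.** **Inputs.** The event, population and exit rules come from sections D, L and N. The protocol gives no share of COVID-19 deaths without admission. Section K reports 36,974 COVID-19 deaths in England in wave 1 (36,974 / 56,550,000 = 0.065%), without a split by place of death or admission. Table 1 sizes whole cohorts and does not bear on this point. All shares and risks below are therefore assumptions, with constant hazards.

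**1. Path of the patient.** Positive test, then COVID-19 death, with no admission:
- 2b: no event, exit at death.
- 2c: not in the population.
- Unconditioned 2b: the outcome is still admission and exit is still at death, so not counted.
- Unconditioned 2c: counted as a COVID-19 death.
- Selection-bias analysis for 2c: enters the probability of admission among those who died, by exposure.
- Selection-bias analysis for 2b: not addressed.

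**2. Effect on the 2b HR.** Let u be the share of first severe events (admission, or COVID-19 death without admission) that are deaths without admission. Then

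2b HR = composite HR × (1 − u_ICS) / (1 − u_comparator).

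With a composite HR of 1.00:

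| u, ICS | u, comparator | 2b HR | 2b HR if shares are swapped |
|---|---|---|---|
| 5% | 5% | 1.00 | 1.00 |
| 10% | 5% | 0.90/0.95 = 0.95 | 1.06 |
| 20% | 5% | 0.80/0.95 = 0.84 | 1.19 |
| 20% | 10% | 0.80/0.90 = 0.89 | 1.13 |
| 30% | 10% | 0.70/0.90 = 0.78 | 1.29 |

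Counting the unadmitted COVID-19 deaths as events returns 1.00 in every row.

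**3. Composite against admission alone.** Assume comparator risks of 20% for admission and 10% for unadmitted death, with ICS hazard ratios of 0.85 and 1.5 respectively. Then 2b returns 0.85 by construction, and the composite HR is (0.85 × 0.20 + 1.5 × 0.10) / 0.30 = 1.07. With 5% unadmitted deaths it is (0.85 × 0.20 + 1.5 × 0.05) / 0.25 = 0.98.

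**4. 2c before bias adjustment.** Assume that 20% of test-positives have severe disease and 8% die, in both groups, with 20% (ICS) and 5% (comparator) of the deaths unadmitted.
- ICS: admitted 0.20 − 0.08 × 0.20 = 0.184; deaths among them 0.08 × 0.80 = 0.064; fatality 34.8%.
- Comparator: admitted 0.20 − 0.08 × 0.05 = 0.196; deaths among them 0.08 × 0.95 = 0.076; fatality 38.8%.
- Ratio 0.90, although total COVID-19 mortality is equal.

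**5. Kaplan-Meier against cumulative incidence.** With true risks of 20% (admission) and 10% (unadmitted death), the total cumulative hazard is −ln(0.70) = 0.357, of which 2/3, or 0.238, is admission. One minus Kaplan-Meier is 1 − exp(−0.238) = 21.2%, against a true 20.0%. With 30% and 15%: −ln(0.55) = 0.598; 2/3 is 0.399; 1 − exp(−0.399) = 32.9%, against 30%.

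**The case against.** The strongest reply is that removing a patient from the risk set at death is correct for a cause-specific hazard of admission. That stands: the 2b model is not invalid, and the issue is how its result is read.

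A second reply is that the plan already deals with 2c. This also largely stands. The selection-bias analysis in section P estimates admission probabilities among those who did and did not die, by exposure, from linked ONS deaths, and the unconditioned death analysis counts these deaths. The distortion in step 4 applies to the unadjusted conditional estimate. In-hospital deaths remain in 2c throughout.

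Third, the 2b model is propensity-weighted on age, comorbidities and exacerbations, and the unmeasured-confounding analysis covers 2b as well. Both may reduce an imbalance between the groups, but neither turns the unadmitted deaths into events. Censoring weights would not do so either.

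A reader might infer that the worst outcomes vanish from the study, that the patient who died is handled like one who recovered, or that 2b will show false protection or the wrong sign. The documents support none of these. Only COVID-19 deaths without admission are lost, and only from the conditional steps. A recovered patient stays at risk, whereas one who died leaves the risk set. With equal shares and a composite HR of 1.00 the 2b HR is unchanged, and with a higher share among comparators it rises above 1. In step 3 the value 0.85 is an input. The composite crosses 1 only in the first case; at 5% unadmitted deaths it is 0.98, on the same side as 0.85.

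Finally, making the composite the main 2b outcome would merge stages that the aim keeps apart. That is a fair reason to keep it secondary.

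**Conclusion.** The point holds for 2b in a limited form. COVID-19 deaths without admission are censored there, and no stated analysis shows them: the selection-bias work for 2b concerns missed infections, and its unconditioned version still ends at death. The 2b HR remains a valid cause-specific HR for admission. Read as an effect on severe disease or on the risk of hospitalisation, it can mislead in either direction if the share of unadmitted COVID-19 deaths differs by exposure. Under the assumed shares and a composite HR of 1.00, the range is 0.78 to 1.29. The protocol gives nothing from which to fix the actual size, and it could be negligible.

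The Kaplan-Meier point is firmer because it needs no difference between groups. The plot overstates the probability of admission whenever deaths without admission occur, by 1.2 and 2.9 percentage points in the two illustrations.

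**What to change.** Keep admission as the 2b outcome and make three additions or changes:

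- Co-report a secondary composite of COVID-19 admission or COVID-19 death without prior admission.
- Tabulate COVID-19 deaths without admission by exposure group, in each cohort and wave. If they are few or balanced, the question about the HR closes.
- For the admission outcome, replace Kaplan-Meier with Aalen-Johansen cumulative incidence, with death as a competing event.

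In the text for 2b, describe the Cox result as a cause-specific HR for admission.

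The cost is one derived endpoint, one table and a different plot, since HES and ONS deaths are already to be linked. The drawback is that the composite mixes two stages of the pathway, so it is reported alongside admission and does not replace it.
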